**Baseline:** The Baseline visit will be scheduled within 4 weeks of the Screening visit. The Baseline visit consists of 2 separate appointments within a week of each other. During the first visit, vital signs will be obtained, a brief physical examination will be performed, concurrent medications will be recorded, a blood draw will be performed for measurement of plasma lipids and inflammatory markers, and an LP will be performed as described in detail below.

During the second baseline visit, the neurocognitive test battery will be administered and behavioral assessments will be performed. Comorbid PTSD will be assessed with the CAPS. A detailed description of all study instruments is below.

**Randomization, titration, and continued study treatment:** Upon completion of all baseline procedures, participants will be randomized to receive simvastatin or placebo. Stratification factors will include age (<40 vs ≥ 40 years), gender, and number of blast trauma exposures (<5 and ≥5). Permuted block randomization will be used within each stratum. Varying the block size reduces the predictability of treatment assignment. Separate blocked sequences will be generated for each of the three strata and provided directly to the Research Pharmacist at the VA Puget Sound, who will prepare study drug for dispensing.

Simvastatin will be started at 20 mg qhs and titrated over 2 weeks to a final dose of 40 mg qhs. Placebo will be titrated at week 2 correspondingly. We assume a drop-out rate of ten percent, yielding a total sample size of 50 subjects per group at the end of the study.

**Safety and compliance visits:** Four additional visits will be scheduled at 6 weeks and at 3-, 6-, and 9-months of treatment to monitor adverse effects, assess compliance with study medications, and dispense study medication. Each visit will include measurement of vital signs, update of concurrent medications, and any self-report of adverse effects. Pill counts will be used to assess compliance. Safety assessments as described below will be performed.

**Outcome assessment:** Outcome assessments will be obtained in two visits at the end of 12 months of treatment. Procedures for outcome assessments duplicate the procedures performed during the Baseline visits as described above. Pill counts will be used to assess compliance with medication use.

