**Behavioral, functional and quality of life measures:** The SCID-IV will be administered at screening only to rule out exclusionary psychiatric conditions. Comorbid PTSD will be assessed using the CAPS at baseline and after 12 months of treatment and the PCL-M at all study visits. Current mTBI symptoms, functional status, and health-related quality of life will be quantified using the Brief Symptom Inventory (BSI), the Rivermead Postconcussive Questionnaire (RPQ), the Neurobehavioral Symptom Inventory (NSI), Satisfaction with Life Scale (SWLS) and the Craig Handicap and Assessment Reporting Technique (CHART-DF). The PHQ-9 and AUDIT-C will be administered at all study visits to assess depressive symptoms and alcohol use.

**Neurocognitive Battery:** We will use measures from the NINDS CDE as well as additional measures for assessment of neurocognitive function. The neurocognitive test battery includes measures of learning and memory, attention and information processing speed, and executive function. In addition, we will employ a measure of test effort (the Test of Memory Malingering [TOMM]) to provide an estimate of the validity of subject's test scores. If a subject's score on the TOMM suggests inadequate test effort, the rest of neurocognitive test scores will be considered invalid. The estimated time to complete the entire test battery is two hours. The complete neurocognitive battery will be administered at baseline and after 12 months of treatment with simvastatin or placebo. A brief global cognitive screening measure (the MoCA) will be administered at screen and at all subsequent study visits to ensure there is no cognitive decline during the study. The study psychometrist will be trained by Co-Investigator, [name]., MIRECC neuropsychologist, and she will conduct periodic checks for adherence to the standardized neuropsychological test battery administration protocol.

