### **Data Analysis:**

**Specific Aim 1:** To examine the effects of 12 months of treatment with simvastatin 40 mg/day on CSF concentrations of tau biomarkers (t-tau, p-tau181, and t-tau:p-tau181 ratio) and brain-derived neurotrophic factor (BDNF) in Iraq and Afghanistan Veterans with repetitive blast concussion mTBI.

**Hypothesis 1:** Compared to placebo, simvastatin will reduce levels of CSF t-tau, p-tau181, and p-tau181:t-tau ratio; and will increase level of CSF BDNF.

**Specific Aim 2:** To explore the effects of 12 months of treatment with simvastatin 40mg/day on CSF A $\beta$ 42, and biomarkers of oxidative stress and neuroinflammation in Iraq and Afghanistan Veterans with repetitive blast concussion mTBI.

**Hypothesis 2:** Compared to placebo, simvastatin will reduce levels of CSF A $\beta$ 42, and biomarkers of oxidative stress (F2-isoprostanes) and neuroinflammation (interleukin-6 [IL-6], IL-8, and S100 $\beta$ ).

**Sample Size, Effect Size, and Power** are based on the change from baseline in the CSF t-tau, p-tau181, and BDNF (Specific Aim 1). We will recruit 120 subjects for this study. Assuming a drop-out rate of about 17%, there will be approximately 50 subjects per treatment group (simvastatin vs. placebo). Using an overall Type I error rate of 5% and a Bonferroni adjustment based on four primary endpoints: CSF t-tau, p-tau181, p-tau181:t-tau ratio, and BDNF (i.e., setting  $\alpha = 0.05/4 = 0.0125$ ), 50 subjects per treatment group yields 80% power to detect an effect size (i.e., | Mean | / SD) of 68% and 90% power to detect an effect size of 77%. For the preliminary study of statin treatment described in Preliminary Findings, change from baseline in t-tau was -107 pg/ml (SD = 129 pg/ml), yielding an observed effect size of 83%.

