### **Statistical analysis.**

**Primary analysis plan:** All CSF biomarkers, neuropsychological test scores, behavioral assessments, and functional and quality of life measures are continuous variables. Gender, APOE genotype, and number of mTBIs ( $\geq 5$  or  $< 5$ ) are categorical. Analysis of covariance (ANCOVA) will be used to assess the change from the baseline in all biomarkers as well as neuropsychological test scores. All outcomes are continuous variables. The distribution of model residuals will be assessed and outcome variables may be transformed to conform to assumptions of the statistical tests (e.g., for non-normality). The response variables will be biomarker concentrations at the end of the study (12-month visit), and predictor variables will include biomarker concentrations at the beginning of the study (baseline visit), treatment arm assignment (simvastatin vs. placebo), as well as the variables that were used for stratification of treatment assignment (i.e., gender and number of blast exposures). To examine effects of statin treatment on memory and cognition, the response variables will be test scores at the end of the study (12-month visit). The predictor variables will include test scores at the beginning of the study (baseline visit), treatment arm assignment (simvastatin vs. placebo), as well as the variables that were used for stratification of treatment assignment (i.e., gender and number of blast exposures). Significance of treatment arm effect will be adjusted for multiple tests (i.e., the four primary endpoints) using the method of Holm (1979).

The primary analysis will include all subjects who were randomized and completed the study. A secondary analysis will use a linear mixed-effects model to include all subjects who were randomized and had a baseline visit, including subjects with just a baseline visit as well as subjects with a baseline visit and an early termination visit. Baseline differences, if any, between study completers and non-completers will be summarized.

**Secondary analysis plan:** In addition to the above primary analysis, secondary analyses will include the following:

- Correlation analyses to assess relationships among CSF biomarkers and how they change over time relative to each other.
- Exploring what other covariates (such as serum cholesterol levels) may be important in predicting changes from baseline in CSF AD biomarkers

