Available prospective, randomized, double-blind, placebo-controlled trials have provided scant evidence of statin-induced cognitive impairment as assessed by formal neuropsychological testing. In a study of 209 hypercholesterolemic adult subjects treated with lovastatin 20 mg/d or placebo for six months, Muldoon et al. found that the statin-treated subjects showed slightly less improvement over time in comparison to placebo-treated subjects on tests of attention and psychomotor speed, but did not differ on tests of mental flexibility, working memory or memory retrieval. In a follow-up study comparing placebo, simvastatin 10 mg/d, and simvastatin 40 mg/d, the same pattern of lesser improvement in simvastatin vs. placebo-treated subjects was seen only on some tests of attention and psychomotor speed but not on others. However, four independent studies did not find any differences in performance on a broad range of neuropsychological tests between those treated with BBB crossing statins and those treated with non-BBB crossing statins. Finally, Gibellato et al. studied 136 middle-aged military aircrew personnel treated with placebo, pravastatin 40 mg/d, or simvastatin 40 mg/d for 28 days and found no effects on performance on a battery of computerized tests demonstrated to be sensitive to detecting subtle impairments in complex cognitive processes involved in piloting aircraft (the Federal Aviation Administration CogScreen Aeromedical Edition).

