The prospective trials of statin effects on neuropsychological measures of cognition all had small sample sizes and may therefore have been underpowered to detect changes in cognitive function. However, secondary analyses of data from the Heart and Estrogen/progestin Replacement Study of 1037 postmenopausal women found that declines in MMSE scores over four years of follow up were less in statin users versus non-users. The larger Cardiovascular Health Study of 3,334 patients found a trend towards lesser declines in Modified Mini-Mental State Examination (3MS) scores in statin users versus non-users with hypercholesterolemia. Of note, the overwhelming majority of subjects in these studies were elderly at the time of enrollment and therefore at elevated risk of experiencing cognitive adverse effects of statins. That these elderly subjects did not demonstrate cognitive adverse effects of statins argues strongly for their safety in other vulnerable populations, such as Iraq and Afghanistan Veterans with repetitive mTBI.

The absence of short-term changes in cognitive function in these large N studies argues persuasively that the effect sizes of any potential adverse cognitive effects must be exceedingly small. As cogently stated in a recent review of statin safety, "These measurements in large numbers of participants in randomized trials establish beyond doubt that statins cause no perceptible decline in cognitive function". Consistent with this low rate of adverse events, simvastatin was approved for over-the-counter sale in the United Kingdom in 2004. In addition, a US Neurology Expert Panel charged with the task of reviewing the scientific evidence related to adverse effects of statins recently concluded that statins do not impair memory or cognitive function; however, this expert panel also recommended that "investigation of statins should include secondary outcome measures that address potential adverse events," we will monitor subjects in our study for changes in cognitive function by means of a brief global cognitive scale at the 6 week and 3- 6- 9- and 12-month visits.

**Risks of venipuncture:** Removal of blood by a needle and Vacutainer or syringe poses a small risk of pain or bruising at the site of the needle stick. Infrequently, subjects may experience fainting or dizziness and there is also a slight risk of infection at the site of the needle stick.

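### Cognitive harm is analysed score by score over at least 12 scores with about 50 per arm and no lead analysis; a pre-specified attention/psychomotor-speed composite would give one interpretable estimate, with more power only if decline is spread over most of its tests

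*Combined protocol and SAP*

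**What the plan says.** The Statistical analysis section states: "Analysis of covariance (ANCOVA) will be used to assess the change from the baseline in all biomarkers as well as neuropsychological test scores". For cognition it adds "To examine effects of statin treatment on memory and cognition, the response variables will be test scores at the end of the study", with the baseline score, arm, gender and number of blast exposures as predictors. It names no composite, domain score or key cognitive measure. Holm's method is applied to the four primary CSF endpoints only, and no multiplicity rule is stated for cognitive scores. The main analysis uses randomised participants who completed the study. A secondary mixed model also takes in early-termination visits.

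On the battery: "The neurocognitive test battery includes measures of learning and memory, attention and information processing speed, and executive function". The list of study instruments gives at least 12 scored tests. They are Letter-Number Sequencing, Grooved Pegboard, Consonant Trigrams, simple reaction time, choice reaction time, Continuous Visual Memory, Digit Vigilance, RAVLT, Processing Speed Index, Digit Span, COWAT and Trail Making. This count leaves out the MoCA, the WTAR (premorbid estimate) and the TOMM (effort check).

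The power statement under Data Analysis concerns the CSF endpoints: "Using an overall Type I error rate of 5% and a Bonferroni adjustment based on four primary endpoints". It expects 50 per arm: "Assuming a drop-out rate of about 17%, there will be approximately 50 subjects per treatment group (simvastatin vs. placebo".

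Under Risks of Simvastatin, the plan says that earlier prospective statin trials with cognitive testing "all had small sample sizes and may therefore have been underpowered to detect changes in cognitive function". In one simvastatin trial, the smaller improvement relative to placebo "was seen only on some tests of attention and psychomotor speed but not on others".

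**The concern.** The Specific Aims give concern about adverse effects as the reason for the battery, so the cognitive comparison has a job to do. The plan recognises that earlier trials may have lacked power and that the earlier signal lay in attention and psychomotor speed. It then uses a test-by-test analysis of modest size without saying which result would carry the conclusion. If one or two scores reach p < 0.05, nothing in the plan separates chance from harm. If none does, a row of non-significant tests gives little reassurance. For the CSF markers the plan adds a Fisher's exact comparison aimed at small but consistent declines. It has no counterpart for consistency across cognitive tests.

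**Working it through.** **Inputs from the documents.** 50 per arm (Data Analysis); 12 scores (counted above); retest correlation r = .51-.70, quoted for the RAVLT and the only such range given for a scored test.

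**Assumptions not in the documents.** True effect 0.3 SD; nominal two-sided 5% per cognitive score; the same r for every test; correlation ρ between baseline-adjusted scores of 0-.6 for chance findings and .3-.5 for the composite.

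**1. The plan's own figure.** With n = 50 per arm, two-sided α = 0.05/4 = 0.0125 and the noncentral t, power is 80.2% at 0.68 SD and 90.2% at 0.77 SD. The stated 80% and 90% are reproduced. No power is stated for cognition.

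**2. Power of one cognitive test.** Adjusted effect d = 0.3/√(1−r²); noncentrality = d × √(50/2) = 5d.

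| r | d | 5d | power | missed |
|---|---|---|---|---|
| .51 | 0.3/0.860 = 0.349 | 1.74 | 41% | 59% |
| .60 | 0.3/0.800 = 0.375 | 1.88 | 46% | 54% |
| .70 | 0.3/0.714 = 0.420 | 2.10 | 55% | 45% |

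The effect detectable with 80% power is 2.80 × √(2/50) × √(1−r²), or 0.48 SD at r = .51 and 0.40 SD at r = .70.

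The number per arm is itself uncertain. The randomisation section says "We assume a drop-out rate of ten percent, yielding a total sample size of 50 subjects per group at the end of the study", but 10% of 120 leaves 108/2 = 54 per arm, while 17% leaves about 50. Scores are also discarded when the effort test is failed. Power is 43-58% with 54 per arm and 37-50% with 45.

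**3. Chance findings among 12 scores with no drug effect.** If independent: 1 − 0.95¹² = 46%; in the harm direction, 1 − 0.975¹² = 26%. With equally correlated test statistics (simulation):

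| ρ | at least one of 12 | harm direction |
|---|---|---|
| 0 | 46% | 26% |
| .3 | 40% | 20% |
| .5 | 32% | 16% |
| .6 | 28% | 14% |

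**4. Composite of k tests, m of which fall by 0.3 SD.** Effect = (m/k) × d / √((1+(k−1)ρ)/k), 50 per arm, two-sided 5%, noncentral t.

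- All fall, least favourable (k = 4, r = .51, ρ = .5): 0.349/√(2.5/4) = 0.441, power 59%.
- All fall, most favourable (k = 6, r = .70, ρ = .3): 0.420/√(2.5/6) = 0.651, power 90%.
- Half fall: these effects are halved, to 0.22 and 0.33, and power is about 20-36%.
- One falls: from 0.349/6/√(3.5/6) = 0.076 (k = 6, r = .51, ρ = .5) to 0.420/4/√(1.9/4) = 0.152 (k = 4, r = .70, ρ = .3), power 7-12%.

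**5. Precision.** The 95% CI half-width for one test is 1.984 × 0.2 × √(1−r²), or 0.28-0.34 SD. Multiplying by √((1+(k−1)ρ)/k), which runs from 0.65 to 0.79 in the two all-fall cases above, gives 0.18-0.27 SD for the composite.

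**The case against.** Cognition here is safety monitoring in a proof-of-concept trial sized for CSF markers. Unadjusted safety tests are usual, and low power for them is no error. Participants are protected individually, by the MoCA at safety visits, the full battery on a trigger, and termination rules. All of this stands, and it makes the point an improvement rather than a correction. But individual rules do not estimate a difference between arms, and no between-arm MoCA analysis is specified.

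A reader might infer that a composite cures both the low power and the chance findings. The documents do not support that. The earlier pattern they describe touched some attention and speed tests and not others. With half the components affected, the composite's 20-36% is below the 41-55% of a single affected test. Nor does the composite rescue smaller effects: 0.15 SD on every component gives the same mean shift as 0.3 SD on half, hence the same 20-36%. The plan reports slightly less improvement in earlier trials and argues that any effect must be very small, so 0.3 SD is not its expectation.

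A reader might also infer that the trial as a whole has about even odds of missing cognitive harm. The 45-59% is per test. If all 12 scores fell by 0.3 SD, at least one would be nominally significant 83-98% of the time (ρ = .3-.6). The difficulty is that such a hit also appears in 28-46% of trials with no effect.

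Finally, a composite on completers inherits a selection problem. Participants who decline cognitively are removed, and the main ANCOVA then leaves them out, so a tighter interval could reassure falsely. This objection stands and shapes the fix.

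**Conclusion.** The point holds as a gap in pre-specification: at least 12 cognitive scores, about 50 per arm, no lead analysis and no multiplicity rule for these scores. Under the stated assumptions each test misses a 0.3 SD effect about 45-59% of the time, and 28-46% of trials without a drug effect show at least one nominal finding (14-26% towards harm). A domain composite supplies one interpretable estimate with a narrower interval. It gains power, to about 59-90%, only if decline is spread over most of its components. These figures depend on 0.3 SD, on a retest range quoted for one test only, and on adjusted scores correlating .3-.5. It is a worthwhile, cheap improvement and does not affect the CSF conclusions.

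**What to change.** Before unblinding, add a paragraph to the analysis plan:

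- **Lead cognitive safety estimate:** the mean z-score of the attention and psychomotor-speed tests already in the battery, for example Grooved Pegboard, simple and choice reaction time, Digit Vigilance, Processing Speed Index and Trail Making. Name the exact score from each, since some tests give several. Standardise to the pooled baseline mean and SD, and reverse timed scores so that higher is better. Use the planned ANCOVA and report a 95% CI. The plan's text justifies the domain in advance: it locates the earlier signal there, calls the Pegboard sensitive to statins, and calls the reaction-time battery sensitive to medications and mild head injury.
- **Supportive:** a memory composite built the same way, and all single-test ANCOVAs, unadjusted and labelled so. The single tests must stay, because the composite is weak against harm confined to one or a few tests.
- **Decliners:** report the lead composite also from the mixed model already planned, which includes early-termination visits.

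Two sets of passages need reconciling. The cognitive termination rule reads differently under Monitoring safety of participants (two measures), Criteria for termination (more than one component) and Protection Against Risk (any test). The drop-out rate is given as both 10% and about 17%.

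The cost is a paragraph of wording and minor programming. No new data are needed and no planned analysis is replaced.

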**Monitoring safety of participants:** Simvastatin is used widely for lowering cholesterol and for primary prevention of cardiovascular and cerebrovascular disease at the doses proposed in this application. It is generally safe and well tolerated. The rate of adverse reactions necessitating withdrawal from statin therapy is <1% in clinical practice. The most common adverse effects in clinical use are elevated liver transaminases, myalgias, and elevated CPK. In our pilot study, all subjects tolerated a final simvastatin dose of 40mg/day. Of 24 subjects recruited, only two had significant adverse effects in response to statin therapy. One experienced significant myalgias requiring discontinuation of therapy despite a non-significant elevation in CPK. Another exhibited a slight increase in CPK with statin therapy. Mean serum CPK concentrations increased marginally over the course of the study. Mean SGOT and SGPT values increased equivalently. Only one subject developed a significant, though asymptomatic, elevation in SGPT. None of the subjects in our pilot study nor in our current placebo-controlled trial of simvastatin for primary prevention of AD experienced adverse cognitive changes or psychiatric symptoms.

Subjects will be advised of potential drug-related side effects such as muscle pain and weakness and nausea or vomiting at both the Screen (consent process) and Baseline visits. In addition, subjects will be monitored at 6 weeks and at 3-, 6-, 9-, and 12 months of treatment for potential adverse events. At each visit, we will review symptoms of anticipated adverse effects (such as muscle pain, weakness, and nausea), measure LFTs, CPK, and HbA1c, and (for female subjects of childbearing potential) conduct urine pregnancy tests.

To monitor for potential cognitive side effects, we will perform the MoCA (a brief but sensitive global cognitive test) at all safety visits. If a subject reports problems with memory or cognitive function after initiation of study medication sufficient to interfere with daily function or MoCA score decline of one standard deviation or greater compared to Baseline, we will perform a thorough neurological and psychiatric examination and will administer the entire neuropsychological battery. If a decline of one standard deviation or greater compared to Baseline is present on two neuropsychometric measures, the subject will be terminated from the study.

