To monitor for emergence or worsening of comorbid depression, the PHQ-9, a self-report measure of depression will be administered at all visits. The PHQ-9 score can range from 0 to 27. Scores of 5, 10, 15 and 20 represent thresholds demarcating the lower limits of mild, moderate, moderately severe and severe depression, respectively. If the PHQ-9 score is increased by 10 (i.e., an increase of two severity categories) compared to baseline, the subject will be terminated from the study. To monitor alcohol use and symptoms of comorbid PTSD, we will administer the AUDIT-C and the PCL-M at all visits.

If at any time during the study, a participant complains of symptoms which may indicate a potential adverse event, additional safety visit(s) as necessary will be performed. Procedures to be performed at additional visits will depend on the symptoms the participant is experiencing. If the participant meets any criterion for study removal (as described below), an early discontinuation visit will be performed.

**Early treatment discontinuation procedures:** The primary reasons for treatment discontinuation anticipated during the study are adverse effects, protocol violation, noncompliance, and withdrawal of consent. We will make every reasonable effort to keep each subject in the study. Every effort will be made to schedule a discontinuation visit as soon as possible following discontinuation of study medication to allow collection of outcome and safety measures.

**Criteria for termination from study:** Subjects will be removed from the study if they: 1) develop a significant adverse medication reaction, including psychiatric adverse effects; 2) exhibit >1 standard deviation decline on more than one component of the neuropsychological test battery; 3) develop a significant elevation in serum transaminases (i.e., > 3 X upper limit of normal for SGOT and/or SGPT) or CPK (i.e., > 10 X upper limit of normal); 4) have a positive urine pregnancy test; or 5) meet NCEP/ATP-III criteria for initiation of lipid-lowering therapy at the 3- or 6-month safety visits.

**Compliance with study medications:** Subjects will be given a 6-week supply of medication at Baseline and at the 6-week visit, and subjects will be given 3-month supplies of medication at the 3-, 6- and 9-month

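### The MoCA is collected at five on-treatment visits, but no between-arm comparison of the four interim scores is specified

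*Combined protocol and SAP*

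**What the plan says.** *Schedule.* Under Risks of Simvastatin, the protocol cites an expert panel's advice that statin studies carry outcome measures for possible adverse events. It answers that subjects will be monitored for cognitive change "by means of a brief global cognitive scale at the 6 week and 3- 6- 9- and 12-month visits". The MoCA row of Table 3 agrees: screening, second baseline visit, 6 weeks, 3, 6 and 9 months, and the first 12-month visit.

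*Use of the interim scores.* Under Monitoring safety of participants, "we will perform the MoCA (a brief but sensitive global cognitive test) at all safety visits". A self-reported problem that interferes with daily function, or a "MoCA score decline of one standard deviation or greater compared to Baseline", leads to an examination and the full battery, and possibly to termination. Protection Against Risk repeats this trigger.

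*Analysis.* In the Primary analysis plan under Statistical analysis, the model for memory and cognition is an ANCOVA in which "the response variables will be test scores at the end of the study (12-month visit"), with baseline score, arm, gender and number of blast exposures as predictors. On the analysis set: "The primary analysis will include all subjects who were randomized and completed the study". A secondary linear mixed-effects model adds subjects who have only a baseline visit, or a baseline and an early termination visit. It does not name the scheduled safety visits, and the Secondary analysis plan lists no longitudinal MoCA comparison.

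*Battery.* "The complete neurocognitive battery will be administered at baseline and after 12 months of treatment with simvastatin or placebo". The same section describes the MoCA separately, as a brief screening measure.

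**The concern.** The MoCA is offered as the answer to a call for outcome measures on cognitive harm, and an outcome measure informs about treatment only when the arms are compared. A trigger applied to one subject at a time cannot separate a drug effect from ordinary fluctuation. Four of the five on-treatment MoCA scores have no stated role beyond that trigger.

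Two consequences follow. A harm present in the first months and gone by 12 months would be missed by a 12-month test. And subjects terminated for cognitive decline drop out of the completer comparison, although their interim scores have already been collected. The protocol itself notes that earlier trials of statins and cognition may have been underpowered, so a conclusion of no cognitive harm should not leave collected data out.

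**Working it through.** **1. The plan's own figure.** Sample Size, Effect Size, and Power gives 50 per arm and alpha = 0.05/4 = 0.0125, with 80% power at 0.68 SD and 90% at 0.77 SD. The standard error of a standardised difference is √(2/50) = 0.20, and the two-sided critical value is 2.498.

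- 0.68 SD: 0.68/0.20 − 2.498 = 0.902, power 81.7% (80.2% with the noncentral t).
- 0.77 SD: 0.77/0.20 − 2.498 = 1.352, power 91.2% (90.2% with the noncentral t).

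The figures reproduce with a two-sided test. They concern CSF endpoints; no power is given for cognition.

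**2. Assumptions for the MoCA.** 50 per arm, from the plan. Two-sided alpha 0.05, because the plan gives none for cognition. Compound symmetry with correlation ρ from 0.5 to 0.8, baseline included. Effects are in SD units, because no MoCA SD is given.

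**3. Residual variance given baseline.** One visit: 1 − ρ². Mean of five visits: (1 + 4ρ)/5 − ρ². The standard error of the arm difference is √(2v/50), and the difference detectable with 80% power is 2.80 × SE.

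| | ρ = 0.5 | ρ = 0.8 |
|---|---|---|
| Variance, 12 months only | 0.75 | 0.36 |
| Variance, five-visit mean | 0.60 − 0.25 = 0.35 | 0.84 − 0.64 = 0.20 |
| Ratio | 0.47 | 0.56 |
| SE, 12 months / mean | 0.173 / 0.118 | 0.120 / 0.089 |
| Detectable difference, 12 months / mean | 0.49 / 0.33 SD | 0.34 / 0.25 SD |

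**4. Power = Φ(effect/SE − 1.96), by pattern of harm.**

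- *Constant 0.3 SD.* 12-month score: 41% (ρ = 0.5) to 71% (ρ = 0.8). Five-visit mean: 72% to 92%.
- *Transient: 0.5 SD at 6 weeks, 3 and 6 months, none at 9 and 12 months.* The mean effect is 3 × 0.5/5 = 0.30 SD, so the five-visit mean again has 72% to 92%. The 12-month test rejects only at its 5% alpha.
- *Rising linearly to 0.4 SD at 12 months.* The mean effect is 0.4 × (1.5 + 3 + 6 + 9 + 12)/60 = 0.4 × 0.525 = 0.21 SD. Five-visit mean: 43% to 65%. 12-month score: 64% to 92%.

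**5. Loss of decliners from the completer set.** This was simulated with 2,000 runs per setting, 60 randomised per arm, 17% random dropout and a constant 0.4 SD harm. A share of subjects with an interim MoCA fall of 1 SD or more is terminated.

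| Share terminated | Completer estimate, ρ = 0.6 / 0.8 | Power, ρ = 0.6 / 0.8 |
|---|---|---|
| none | 0.40 / 0.40 SD | 67% / 91% |
| half | 0.38 / 0.36 SD | 55% / 79% |
| all | 0.29 / 0.29 SD | 28% / 56% |

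The last row is an upper bound, since the protocol requires the battery before termination. With all such subjects terminated, averaging the available visits in all randomised subjects gives 92% (ρ = 0.6) or over 99% (ρ = 0.8). That crude average overstates the harm slightly (0.43 to 0.44 SD). It is not the model proposed below, and it shows only how much information is left out.

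**The case against.** The strongest case against is that the MoCA is a screening tool. The Overview assigns cognitive adverse effects to psychometric measures taken at baseline and 12 months, and for those the 12-month ANCOVA uses every scheduled on-treatment score. This stands. A reader might infer that cognitive safety as a whole loses four of five measurements; the documents do not support that.

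Nor are the interim scores shut off from every arm-level view. The discontinuation visit collects outcome and safety measures, and an early termination score can enter the secondary mixed model. The monitoring board receives data coded by arm and reviews safety annually. A reader should therefore not infer that an early harm could appear nowhere. Neither route, however, is said to use the scheduled interim MoCA scores.

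It is also tempting to say that depression and PTSD symptoms are likewise tested only at 12 months. The protocol says "we will administer the AUDIT-C and the PCL-M at all visits", and Table 3 has these scales and the PHQ-9 at five on-treatment visits. But Statistical analysis names its ANCOVA for biomarkers and neuropsychological test scores, and states no between-arm model for these scales at any visit. That is a different gap.

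Finally, averaging is not always better. The protocol's own worry is long-term lowering of brain cholesterol, which fits a harm that builds up, and for that pattern the 12-month test is the stronger one.

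**Conclusion.** The point holds for the MoCA. Its four interim on-treatment scores enter no prespecified arm comparison. Because the MoCA is listed apart from the battery, it is unclear whether even its 12-month score is compared; the 12-month power figures assume that it is.

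The gain is real but depends on the pattern: large for a constant harm, decisive for a transient one, and reversed for one that rises steadily. All figures rest on the assumed correlation, compound symmetry and effect sizes, since the documents give no MoCA SD, correlation or margin. The completer restriction can weaken the 12-month comparison further, by an amount that depends on how many decliners are terminated.

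This is a cheap improvement. Individual monitoring is in place, the battery's ANCOVA is not affected, and neither are the primary CSF conclusions.

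**What to change.** In Statistical analysis, add a mixed model for repeated measures for the MoCA. Use all on-treatment visits from all randomised subjects, with baseline score (state whether screening or second baseline visit), arm, visit, arm-by-visit and the stratification factors. The Randomization paragraph lists age as well as gender and blast exposures, whereas Statistical analysis lists only the last two; settle which apply. Report the arm difference at each visit, keeping the 12-month contrast, and the average over visits, each with a 95% confidence interval. Report by arm the proportion with a 1 SD MoCA decline and the proportion terminated for cognitive reasons.

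The same model can serve the PHQ-9 and PCL-M, which now have no stated between-arm model. Keep the 12-month ANCOVA for the battery.

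The cognitive termination rule also needs reconciling, since it decides who leaves the completer set. Monitoring safety of participants and Criteria for termination refer to two, or more than one, measures; Protection Against Risk refers to any test.

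Cost: plan wording and one extra model per scale, with no new data or visits. The average dilutes an effect that builds up over time, which is why the 12-month contrast must stand beside it.
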